2.2. Primary and Secondary Measures and Endpoints

[figure not shown]
2.2.1. Primary Efficacy Endpoint

The primary efficacy endpoint is the frequency of clinical asthma exacerbations (CAEs) per patient during the 52-week treatment period. Refer to Section 6.2.1 for additional details regarding the definition of CAE.

2.2.2. Secondary Efficacy Endpoints

The secondary efficacy endpoints are as follows:

- change in pre-bronchodilator FEV₁ from baseline/DoR at week 52
- change in Asthma Quality of Life Questionnaire for patients 12 years and older (AQLQ +12) score from baseline/DoR at week 52
- change in 6-item Asthma Control Questionnaire (ACQ-6) score from baseline/DoR at week 52
- change in total asthma symptom scores (day and night) from baseline at week 52
- percentage of asthma control days from baseline/DoR to week 52
- change in St. George's Respiratory Questionnaire (SGRQ) from baseline/DoR at week 32
- time to first clinical asthma exacerbation during the 52-week treatment period
- frequency of exacerbations requiring hospitalization or emergency department visits per patient during the 52-week treatment period
- frequency of moderate exacerbations defined as exacerbations requiring additional asthma controller medication that was not a systemic corticosteroid and that did not result in an asthma-specific hospitalization or emergency department visit during the 52-week treatment period

2.2.4. Target Biomarker Endpoints

The target biomarker endpoints are the blood eosinophil counts at baseline/DoR; weeks 2, 4, 8, 12, 16, 32, 52 or early withdrawal; and the follow-up visit (approximately week 64).

2.2.5. Immunogenicity Endpoints

Samples for immunogenicity assessment for development of anti-drug antibodies will be obtained before the administration of study drug at DoR; prior to study drug administration at weeks 4, 16, 32, 52 or early withdrawal; and the follow-up visit (approximately week 64). Additional samples will be collected at the late follow-up visit (approximately week 76).

2.2.6. Pharmacokinetic Endpoints

The PK endpoints are the serum reslizumab concentrations at baseline/DoR; weeks 1 (patients in US study centers only), 2, and prior to study drug administration at weeks 4, 8, 12, 16, 20, 32, 48, 52 or early withdrawal; and the follow-up visit (approximately week 64). An additional PK sample will be taken at long term follow-up (approximately week 76) at the same time for ADA sample collection.

2.2.8. Safety Endpoints

The safety endpoints for this study are as follows:

- adverse events throughout the study

- vital signs (pulse, respiratory rate, and blood pressure) throughout the study
- concomitant medication usage throughout the study
- physical examination findings throughout the study
- clinical laboratory evaluations at screening, baseline/DoR, and periodically throughout the study
- ECG evaluation at screening and week 24, 36, and 52 or early withdrawal

2.3. Sample Size and Power Considerations

The primary efficacy variable for this study is the frequency of CAEs per patient during the 52-week treatment period. The study will be considered positive if the primary efficacy measure indicates a statistically significant treatment effect of reslizumab versus placebo at the respective predefined significance level.

Power calculations were based on the below assumptions:

- Negative binomial (NB) distribution for the number of exacerbations with a mean of 2.9 exacerbations per patient per year for the placebo group
- Dispersion parameter of 1.2
- Treatment effect of 45% between the reslizumab group and the placebo group
- Alpha level of 0.05

Based on the assumptions above, 225 patients per group (450 total) will provide >90% power to detect significant treatment effect of reslizumab over placebo in the reduction of exacerbation rate. The sample size was increased beyond the sample size required to provide 90% power in order to allow sufficient number of patients to assess safety and immunogenicity and to ensure adequate enrollment in the adolescent subset. The current sample size also provides higher power for other efficacy endpoints.

Patients with blood eosinophil levels of 300/ μ L to <400/ μ L will be limited to no more than 30% of patients (60 patients per treatment group).

2.4. Randomization and Blinding

This is a randomized, double-blind, placebo-controlled study. Patients who meet all inclusion criteria and none of the exclusion criteria will be randomly assigned to receive reslizumab 110 mg sc or matching placebo (approximately 225 patients per treatment group) in a 1:1 ratio. Patients and investigators will remain blinded to treatment assignment during the study. Randomization will be stratified by age (12 to <18 years and \geq 18 years) and blood eosinophil levels at screening (300/ μ L to <400/ μ L and \geq 400/ μ L). This system is used to ensure a balance across treatment groups. The goal is to recruit a maximum of 30% of the patients (60 patients per treatment group) with eosinophil levels of 300/ μ L to <400/ μ L.

The randomization list and treatment will be assigned to the relevant treatment groups through a qualified contract research organization (CRO), eg, via Interactive Voice Response System (IVRS)/ Interactive Web Response System (IWRS). The generation of the medication list and

management of the IRT system will be done by a qualified CRO under the oversight of Teva's Clinical Supply Chain.

The sponsor's clinical personnel involved in the study will be blinded to the study drug identity after the run-in period until the database is locked for analysis and the treatment assignment is revealed, with the exception of the bioanalytical group who will not be blinded to facilitate PK and ADA sample analysis. Eosinophils and monocytes will be redacted from the post-baseline differential cell count reports to avoid the possibility of unblinding patients.

2.5. Sequence of Planned Analyses

2.5.1. Interim Analyses

No interim analysis is planned for this study.

2.5.2. Final Analyses and Reporting

All final, planned analyses identified in this SAP will be performed only after the last patient has completed the study. The randomization codes will not be unblinded until this SAP has been approved.

Any exploratory analyses completed to support study analyses, which were not identified in this SAP, will be documented and reported in appendices to the CSR.

3. POPULATIONS/ANALYSIS SETS

Site [REDACTED] was terminated due to numerous unresolved Good Clinical Practice (GCP) issues, including an overall lack of adequate source documentation (letter to FDA dated 2 December 2016). The data from this site are deemed invalid and the 4 patients randomized at this site will be excluded from the efficacy analysis but will be included as part of the safety analysis. In addition, these patents will be summarized as randomized, but not analyzed, as part of the ITT analysis set in the disposition summary (Section 5.2).

3.1. Intent-to-Treat Analysis Set

The intent to treat (ITT) analysis set will include all randomized patients, with the exception of patients from Site [REDACTED] who will be excluded. In this population, treatment will be based on the treatment to which patients were randomized, regardless of which treatment they actually received.

Two analytic approaches are planned using the ITT analysis set.

- In the first approach, all data collected from patients will be included, regardless of continued adherence to their assigned study treatment.
- In the second approach, data collected from patients during the treatment period will be included, up to the point at which patients discontinue from their assigned study treatment (on-treatment). For patients who completed treatment in this study, the treatment period will be defined from the first dose of study drug to the end of treatment (week 52) visit. For patients who prematurely discontinue treatment, the treatment period will be defined from the first dose of study drug to the last dose of study drug + 4 weeks.

The analytic approach including all data collected from patients will be utilized as the primary approach to analysis for the primary endpoint (frequency of CAE). The on-treatment approach will be conducted as a sensitivity analysis for the primary endpoint. For the analysis of all other efficacy endpoints, the on-treatment approach will be utilized as the main approach to analysis. The analytic approach including all data collected from patients will additionally be conducted as sensitivity analyses for selected secondary endpoints.

3.1.1. ITT Analysis Set (Patients 12-70 Years)

Since AQLQ +12 has only been validated for patients aged 12 to 70 years, the analysis of this variable will be restricted to the subset of the ITT analysis set (excluding patients from Site [REDACTED]) within the specified age range (12 to 70 years) at baseline.

3.2. Safety Analysis Set

The safety analysis set will include all patients who receive at least 1 dose of study drug (including patients from Site [REDACTED]). In this population, treatment will be based upon the treatment patients actually received, regardless of the treatment to which they were randomized. Patients dosed in error, but who otherwise received at least 1 dose of reslizumab, will be assigned to reslizumab for the analysis of safety.

In this analysis, data collected from patients during the treatment period will be included, up to the point at which patients discontinue from their assigned study treatment. For patients who completed treatment in this study, the treatment period will be defined from the first dose of study drug to the end of treatment (week 52) visit. For patients who prematurely discontinue treatment, the treatment period will be defined from the first dose of study drug to the last dose of study drug + 4 weeks. This analysis will be used as the default approach for all safety endpoints.

3.3. Per-Protocol Analysis Set

The per-protocol (PP) analysis set is a subset of the ITT analysis set (excluding patients from Site [REDACTED]) including only patients without major protocol violations. The PP analysis set will only be presented for the primary endpoint. In this analysis, data collected from patients during the treatment period will be included, up to the point at which patients discontinue from their assigned study treatment.

3.3.1. Major Protocol Violations

Table 2 presents the planned list of major protocol violations prospectively identified as having the potential to influence and/or bias the primary efficacy results. A complete list of protocol violations resulting in exclusion of patients from the PP analysis will be determined at the end of the study based on team review of accumulated blinded study data. Updates to the following list will be documented in the minutes from the final Statistical Data Review meeting.

Table 2: Major Protocol Violations

Violation	Approach to identifying protocol violations
Patient does not have ≥ 2 asthma exacerbations within the past 12 months	Inclusion criteria (c); disposition CRF Asthma/allergy history CRF Protocol violation CRF
Patient does not have ACQ-6 score ≥ 1.5 at screening (Visit 1)	Inclusion criteria (d); disposition CRF Asthma control questionnaire CRF Protocol violation CRF
Patient does not have blood eosinophil $\geq 300/\mu\text{L}$ during the screening period (prior to Visit 2)	Inclusion criteria (e); disposition CRF Laboratory data Protocol violation CRF
Patient does not demonstrate FEV ₁ reversibility ($\geq 12\%$) after administration of inhaled SABA	Inclusion criteria (f); disposition CRF Spirometry data Protocol violation CRF Note: Historical reversibility is acceptable.
Patient was not on ICS at baseline (at least a medium total daily dose)	Inclusion criteria (g); disposition CRF Medication CRF Protocol violation CRF
Patient was not on an additional asthma controller medication (eg, LABA, LAMA, LTRA, or theophylline preparations)	Inclusion criteria (h); disposition CRF Medication CRF Protocol violation CRF

Violation	Approach to identifying protocol violations
Patients who were unblinded at any point during the study	Protocol violation CRF
Patients who received the incorrect study treatment at any point during the study	Protocol violation CRF

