Patients will begin screening up to approximately 5 weeks ( $\pm 1$  week) before DoR. During the screening period, a signed and dated informed consent form (and an assent form for children ages 12 through <18 years of age in accordance with local standards) will be obtained before a diagnosis of asthma is confirmed on the basis of patient history and by demonstration of airway reversibility. The patients will also be asked about their asthma medication compliance and to demonstrate their inhaler use technique. If the inhaler use technique is not optimal, patients will be taught the appropriate inhaler use technique during the screening period and should be reassessed before run-in. The patient will also have a complete blood count determined. If the patient's eosinophil count is 300 eosinophils/ $\mu\text{L}$  or greater, and if the patient's medication compliance and inhaler use technique are optimal, the patient will be eligible to continue in the study. Patient medical history, 12-lead ECG, physical examination, hematology and chemistry tests, urinalysis, vital signs measurements, beta-human chorionic gonadotropin serum pregnancy test (for all females of childbearing potential), and concomitant medication history will also be assessed at screening.

To be eligible to enroll in the study, a patient will have an ACQ-6 score of at least 1.5, airway FEV1 reversibility of at least 12% to beta-agonist administration, blood eosinophil count of at least 300/ $\mu\text{L}$ , and a current fluticasone propionate dosage of at least a medium total daily ICS dose with a second asthma controller and will have met all the inclusion and none of the exclusion criteria at screening. The goal is to recruit a maximum of 30% of the patients (60 patients per treatment group) with eosinophil levels of 300/ $\mu\text{L}$  to <400/ $\mu\text{L}$ .

[figure not shown]

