### 4.1. Patient Inclusion Criteria

Patients may be included in this study only if they meet all of the following criteria:

- a. Written informed consent is obtained. A patient 12 through <18 years of age must provide assent, and their parent(s) or legal guardian(s) must provide consent.
- b. The patient is male or female, 12 years of age and older, with a diagnosis of asthma. (Patients 12 to <18 years of age are excluded from participating in South Korea and Argentina, and patients 66 years of age and older are excluded from participating in South Korea.)
- c. The patient has had at least 2 documented asthma exacerbations requiring the use of systemic (oral, intramuscular, or iv) corticosteroids within 12 months of signing the Informed Assent Form/Informed Consent Form.
- d. The patient has an ACQ-6 score of at least 1.5 at screening (visit 1).
- e. The patient has a blood eosinophil level of at least 300/ $\mu$ L during the screening period (ie, before visit 2). (A maximum of 30% of the patients [60 patients per treatment group] with blood eosinophil levels of 300/ $\mu$ L to <400/ $\mu$ L will be enrolled. When this 30% threshold has been reached, only patients with blood eosinophil levels of  $\geq$ 400/ $\mu$ L will then be enrolled.)
- f. The patient has an FEV1 reversibility of at least 12% after administration of inhaled SABA according to standard American Thoracic Society (ATS) or European Respiratory Society (ERS) protocol. Documented historical reversibility within 12 months of signing the Informed Assent Form/Informed Consent Form is acceptable.
- g. The patient has required at least a medium total daily ICS dose based on GINA 2016 clinical comparability table ([Appendix A](#)) for at least 3 months. For ICS/LABA combination preparations, the mid-strength approved maintenance dose in the local country will meet this ICS criterion.
- h. The patient has required an additional asthma controller medication (eg, long-acting beta-2-agonist [LABA], long-acting muscarinic antagonist [LAMA], leukotriene receptor antagonist [LTRA], or theophylline preparations), besides ICS, for at least 3 months or a documented failure in the past 12 months of an additional asthma controller medication for at least 3 successive months.

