### 5.3. Prior and Concomitant Therapy or Medication

Any prior or concomitant therapy, medication, or procedure a patient has had 4 weeks before study drug administration and up to the end of the study period, including follow-up, will be recorded on the CRF. Generic or trade name, indication, and dosage will be recorded. The sponsor will encode all therapy and medication according to the World Health Organization drug dictionary (WHO Drug).

Of note, prior asthma medications such as ICS, leukotriene pathway modifiers, long acting bronchodilators, and mast cell stabilizers may be taken concomitantly and should not be altered

during the study unless patient safety is at risk. Any changes in background maintenance therapy must be discussed with the medical monitor.

The following medications will not be allowed during this study:

- any immunosuppressive or immunomodulatory agents (biological and non-biological), including, but not limited to methotrexate, cyclosporine, and interferon (excluding systemic corticosteroids prescribed for asthma and maintenance allergen immunotherapy)
- all biologic therapies, including, but not limited to omalizumab (Xolair®), mepolizumab, benralizumab, lebrikizumab, and anti-tumor necrosis factor monoclonal antibodies
- all nonbiologic investigational drugs

At each clinic visit after the screening visit, the investigator will ask patients whether they have taken any medications (other than study drug), including over-the-counter medications, vitamins, or herbal or nutritional supplements, since the previous visit. Indication, dosage, and start and end dates should be entered on the appropriate CRF.

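### SAP Table 2's row for inclusion criterion h omits the documented-failure route, so as worded it would class some eligible patients as major violators and drop them from the per-protocol sensitivity analysis

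*SAP*

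**What the plan says.** **Eligibility.** Criterion h (Protocol Section 4.1, repeated in the synopsis) can be met in two ways. One is a need for a second controller on top of ICS lasting 3 months or more. The other is offered as an alternative: "or a documented failure in the past 12 months of an additional asthma controller medication for at least 3 successive months".

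**Violation list.** The matching row of SAP Table 2 reads "Patient was not on an additional asthma controller medication (eg, LABA, LAMA, LTRA, or theophylline preparations", and its sources are given as "Inclusion criteria (h); disposition CRF Medication CRF Protocol violation CRF". The row states no time point, no duration and no exception. The reversibility row of the same table carries a note: "Historical reversibility is acceptable". That note reproduces the alternative allowed by criterion f.

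**Use of the list.** SAP Section 3.3 builds the per-protocol set from ITT patients with no major violation and uses it for the primary endpoint only. SAP Section 6.2.3 names the per-protocol analysis as an on-treatment sensitivity analysis. SAP Section 3.3.1 describes Table 2 as a planned list. The complete list of excluding violations is settled by blinded team review at the end of the study, and updates are minuted.

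**The concern.** A per-protocol analysis is useful because it sets aside patients who departed from the protocol. Protocol Section 11.1.2 counts breaches of key eligibility criteria among the violations, and a patient who meets criterion h by documented failure breaches none. If the row is applied as worded, the per-protocol set loses compliant patients and describes a narrower population, patients taking a second controller, than the trial set out to enrol. A difference between the per-protocol and on-treatment ITT results could then be put down to protocol violations when part of it reflects a change of population.

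Nothing in the SAP shows that the narrowing is intended. Section 10 reports no changes to the protocol-specified analyses. The preface says that the SAP prevails where it differs from the protocol, so the protocol wording does not automatically correct the row.

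**Working it through.** **1. Criterion h against the row's wording**

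| Patient | Meets criterion h? | Fits the row's wording? | Consequence as worded |
|---|---|---|---|
| Second controller for at least 3 months and still on it | Yes | No | Kept |
| Documented failure in past 12 months, now on another second controller | Yes | No | Kept |
| Documented failure in past 12 months, no second controller | Yes | Yes | Removed although eligible |
| No second controller, no documented failure | No | Yes | Removed, correctly |
| On a second controller for under 3 months, no documented failure | No | No | Not caught by the wording |

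The mismatch that matters is the third line.

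**2. The row's sources for the third-line patient**

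- Criterion h and the disposition CRF: the criterion is met, so no flag.
- Medication CRF: shows no second controller, so it flags.
- Protocol violation CRF: depends on what the site recorded; a site applying criterion h has nothing to record.

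The SAP does not say how the three sources combine. Per-protocol membership for this patient therefore depends on an unstated choice.

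**3. Number affected**

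The documents give no count. The planned total is 450 (Protocol Section 9.1). Assume that a share p of patients are of the third-line type:

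- Number removed = 450 × p: 2% gives 9, 5% gives 22.5 (about 22), 10% gives 45.
- Standard error inflation = √(1/(1 − p)): 1.010, 1.026 and 1.054, that is about 1%, 3% and 5%.

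**4. Does power matter?**

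Inputs from Protocol Section 9.1: placebo rate 2.9 per year, dispersion k = 1.2, 45% reduction (rate ratio 0.55, so active rate 2.9 × 0.55 = 1.595), alpha 0.05. The test is two-sided (Section 9.6), with 225 patients per arm. Follow-up is taken as 1 year.

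- V = (1/2.9 + 1.2) + (1/1.595 + 1.2) = 3.372
- Power = Φ(|ln 0.55| × √(n/V) − 1.96)
- n = 225: Φ(0.598 × 8.169 − 1.96) = Φ(2.92) = 99.8%. This reproduces the synopsis figure of more than 99% and is consistent with the more than 90% in Protocol Section 9.1 and SAP Section 2.3.

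Removing the same share from each arm, with rates, effect and follow-up unchanged:

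| Share removed | n per arm | Power |
|---|---|---|
| 2% | 220 | 99.8% |
| 5% | 213 | 99.7% |
| 10% | 202 | 99.6% |
| 30% | 157 | 98.3% |

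The issue is who is in the per-protocol set, not power.

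**The case against.** The strongest reply is that Table 2 is only a planned list, that a blinded review fixes the exclusions, and that the row's first source is criterion h itself. A team that checks eligibility would keep failure-route patients. This stands to the extent that removal is not certain. It does not remove the need for a fix, because the row states the rule prospectively and states it wrongly, and the review is given no instruction on this case.

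A second reply is that the design text describes a population on a second controller. Protocol Section 3.1 does so, but the same sentence runs "with a second asthma controller and will have met all the inclusion and none of the exclusion criteria at screening", so it defers to the listed criteria, which include both routes of h.

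A third reply is that this is one sensitivity analysis of one endpoint. That is correct and sets the severity.

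A reader might also infer stronger points that the documents do not support:

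- *Every failure-route patient is removed.* Only those taking no second controller fit the row.
- *The check cannot see the failure route.* Protocol Section 5.3 limits CRF recording to "Any prior or concomitant therapy, medication, or procedure a patient has had 4 weeks before study drug administration" and onwards. But criterion h is itself a listed source, medication history is a separate visit 1 procedure (Protocol Section 3.16.1), and SAP Section 5.5 defines prior medications without a 4-week limit.
- *The ICS row has the same fault.* Criterion g says of ICS/LABA combinations that "the mid-strength approved maintenance dose in the local country will meet this ICS criterion". It therefore treats that dose as satisfying the medium requirement. The ICS row uses the same medium term and cites g, so it shuts out no eligible route. The missing medium dose for fluticasone furoate in Appendix A creates no conflict with Table 2.
- *The per-protocol result should be read against the primary ITT result.* Those two already differ by design, since the primary analysis includes post-withdrawal data and imputation. The natural comparator is the on-treatment ITT analysis in SAP Section 6.2.3.

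**Conclusion.** The row contradicts criterion h and should be corrected; the severity is minor. Read as written, it classes eligible failure-route patients who take no second controller as major violators and drops them from the per-protocol analysis, unless the blinded review decides otherwise. Reading the row as current use is the natural sense of its wording, but the SAP does not state a time point.

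The effect is confined to the per-protocol sensitivity analysis of the primary endpoint. Its size cannot be computed from the documents: 9 to 45 patients rests on an assumed share of 2% to 10%, and the true number could be close to zero. The primary analysis, the planned 450 patients and the power of the primary comparison are untouched. The power figures for a reduced set assume equal removal from both arms, unchanged rates and effect, and a full year of follow-up. An on-treatment set would have somewhat less follow-up.

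**What to change.** Before unblinding, do one of the following in the criterion h row of SAP Table 2:

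- reword it to *Patient met neither route of inclusion criterion h*; or
- keep the row and add a note parallel to the reversibility one: *Documented failure per inclusion h is acceptable*.

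The first is tighter, because it also brings in the 3-month duration that the present wording leaves out. In either case, state that failure-route patients are identified from the eligibility record and the visit 1 medication history as well as the Medication CRF, so that the absence of a second controller on the Medication CRF does not by itself exclude a patient.

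The cost is one line of SAP wording, or an entry in the minutes of the final Statistical Data Review meeting, plus a blinded check of the patients with no second controller recorded. It needs no new data, no more patients and no change to the primary analysis.
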